Amniochorionic membrane cells in the maternal blood as a biomarker for preterm birth

December 1st 2020

Principal Investigator:

[name], DMSc, Professor
Department of Obstetrics and Gynecology
Aarhus University Hospital
[name]
[name]
[contact]
Email: [contact]

Coordinating Investigator:

[name], PhD-student
Department of Obstetrics and Gynecology
Aarhus University Hospital
[name]
[name]
[contact]
Email: [contact]

Project description

Academic title and name: [name], Medical Doctor

Project title: Amniochorionic membrane cells in the maternal blood as a biomarker for preterm birth

Supervisors

- [name] (main supervisor), Professor, DMSc, Department of Gynecology and Obstetrics, Aarhus University Hospital.
- [name], [name], Department of Gynecology and Obstetrics, University of Texas Medical Branch at Galveston.
- [name], Professor, DMSc, Department of Histopathology, Aarhus University Hospital

Collaborators

- [name], ARCEDI Biotech Aps.
- [name], MBA, ARCEDI Biotech Aps.
- [name], Professor, PhD, Medical University of Graz, Austria.

Aim

The aim of this PhD protocol is 1) to characterize circulating fetal amniochorionic membrane cells (ACM cells) in pregnant women and 2) to investigate if they can function as biomarkers of amniochorionic membrane dysfunction, including risk of preterm birth.

Hypotheses

- 1) It is possible to identify specific cells of the fetal membranes by their protein expression (ACM cells), and confirm the expression and localization of these cells by immunohistochemistry.
- 2) ACM cells can be identified and isolated in maternal blood using the same antibodies that identify the cells in the fetal membranes.
- 3) ACM cells circulating in maternal blood can serve as a biomarker for fetal membrane physiologic or pathologic status.
- 4) The concentration of circulating ACM cells reflects the risk of certain adverse pregnancy outcomes, including Preterm Prelabor Rupture of the Fetal Membranes (PPROM).

Abbreviations

- ACM cells: Amniochorionic Membrane Cells
- PPROM: Preterm Prelabor Rupture of the Fetal Membranes
- PLC: Preterm Labor Contractions

Background

Preterm birth: Globally, preterm birth (15 million per year) is the leading cause of mortality (1 million per year) and morbidity among children under 5 years of age [1]. Important pathways include preterm labor contractions (PLC), Preterm Prelabor Rupture of the Fetal Membranes (PPROM), and iatrogenic

delivery due to preeclampsia and fetal growth restriction [2]. In 2015, the Sustainable Development Goal of the United Nations defined that by 2030 the world should reduce neonatal mortality to at least as low as 12 per 1,000 live births. In order to do so, we must increase our understanding of fetal signaling during parturition in order to tailor better treatments to avoid preterm birth.

ACM cells: The fetal membrane, i.e. the amniochorionic membrane, consists of a single layer of cuboidal amnion epithelial cells, amnion mesenchymal cells (scattered fibroblasts), chorionic trophoblasts, and a collagen-rich extracellular matrix. During pregnancy, the fetal membrane cells multiply, grow and age, which in the end leads to telomere-dependent cellular senescence, labor and human parturition [3, 4]. These changes are expected in membranes at term, but similar features are expected to be seen in cases with PPROM [5].

Recently, in collaboration with ARCEDI Biotech Aps and The University of Texas Medical Branch at Galveston, Aarhus University has identified specific fetal membrane cell markers, i.e. specific proteins highly expressed by the ACM cells. These proteins were identified as followed: mRNA was extracted from fetal membrane cells, and subjected to RNAseq analysis to identify the genes that were differentially expressed as compared to the maternal blood cells. The highest expressed mRNAs and their corresponding proteins were identified. Commercially available antibodies specific for those identified proteins were obtained. These specific antibodies were used for isolating circulating ACM cells from maternal blood from pregnancies carrying male fetuses by Magnetic Activated Cell Sorting (MACS). After isolation, the cells were stained using a fluorescent-labeled pool of cytokeratin antibodies and visualized by scanning microscopy. The individual fetal cells were verified by XY-FISH analysis. Our preliminary studies indicate that circulating ACM cells are present in the second half of pregnancy but not in the first half of the pregnancy (results not yet published).

Nevertheless, we still do not know how the ACM cells are dislocated to the maternal blood. By the use of an advanced histological technique, the laboratory of one of the supervisors, [name], has demonstrated “microfractures” in fetal membranes [6], which may constitute an important source of ACM cells.

We want to confirm by immunohistochemistry that specific antibodies can identify ACM cells in the fetal membranes, and that they can be a platform for isolating ACM cells from maternal circulation by MACS. Identification, quantification, and analysis of ACM cells in the maternal circulation can give us a better understanding of pregnancy physiology and pathophysiology. Furthermore, ACM cells might constitute a new clinical tool for the identification and correct treatment of pregnant women at risk of adverse outcome.

Materials and methods

Study 1: To confirm the protein expression profile of ACM cells by immunohistochemistry

Aim: To confirm that the selected proteins by RNAseq are highly expressed in the fetal membranes, and investigate how specific the expression or expression pattern are for ACM cells.

Hypotheses:

1. The expression or expression pattern of the selected proteins are specific for ACM cells in the fetal membranes and can be used for identification of ACM cells in the maternal circulation.

Materials: 1) Normal fetal amniochorionic membranes. 2) Placental tissue. 3) Multi tissue block containing several types of maternal tissue. 4) Tissue of the placental bed in the uterus collected from placenta previa cesarean sections.

Methods: Immunohistochemistry will be conducted using the specific antibodies previously used for isolation of ACM cells in the maternal circulation. For visualization of antibody binding, standard immunohistochemical protocols will be used. The analysis will be performed on automated staining platforms (Ventana). Interpretation of the staining will be done by bright field microscopy under the supervision of Associate [name], [name], and professor [name], in Texas, Graz, and Aarhus, respectively.

Study 2: Optimizing the method for the isolation of ACM cells from the maternal circulation.

Background: Presently, we use a pool of specific antibodies for markers expressed on the cell surface in both the amnion and chorion to enrich ACM cells from maternal blood.

Aim: We wish to:

1. Evaluate the performance of each antibody to see if it is possible to reduce the number of antibodies used for isolation, in order to make the test more simple and robust.
2. Evaluate if the expression pattern of the selected proteins changes during different gestational ages.

Hypotheses:

1. The antibodies perform differently concerning the number of ACM cells they identify.
2. The expression pattern of the selected proteins do not change during gestation.

Materials:

1. Cross sectional cohort of second and third trimester pregnant women. One blood sample from each woman. The number of participants depends on the results; might be between 10 and 100.
2. Longitudinal cohort of 15 women with normal pregnancies. Blood samples will be collected in gestation weeks 12, 20, 28 and 34, as well as at labor and post partum.

Methods: We will isolate the ACM cells from maternal blood by Magnetic Activating Cell Sorting (MACS) using different specific antibodies for ACM cells. The enriched ACM cells will be stained using fluorescent-labeled cytokeratin and vimentin antibodies, and sorted individually by Fluorescence Activated Cell Sorting (FACS). The true identification of the fetal derived ACM cells will be done by Short Tandem Repeat (SRT) analysis. If appropriate, we will optimize the protocol for the antibodies that perform best and are stable expressed regardless of gestational age.

Study 3: The number of ACM cells in the maternal circulation in normal and pathological pregnancies.

Aim: To evaluate the number of ACM cells in the maternal circulation during pregnancy and at term in normal and pathological pregnancies.

Hypotheses:

1. Normal pregnancies: The number of ACM cells depends on gestational age and increases during labor.
2. Pathological pregnancies: The number of ACM cells is increased above the normal level for the gestational age.

Materials:

1. Longitudinal cohort of normal pregnant women: We will recruit 25 participants at their nuchal translucency scan at 12 weeks gestation. Blood samples will be collected at week 12, 20, 28, 34 and 36. Furthermore, we will collect blood at term, 2 days, and 4, 8 and 12 weeks after birth.
2. Term pregnant women with and without labor contractions: We will recruit 25 women in active labor at the delivery ward and 25 women with planned cesarean sections within a few days.
3. Preterm labor contractions (PLC): We will recruit 25 participants treated at the ward with tocolytics because of preterm labor contractions before 34 weeks gestation.
4. Preterm Prelabor Rupture of the Fetal Membranes (PPROM): We will recruit 25 participants treated at the ward because of PPROM before 34 weeks gestation.
5. Control group: We will recruit 25 women at gestation week 25+0 to 37.

Methods: The ACM cell analyses will be assessed according to the protocol developed in study 2. From these blood samples, we will establish a biobank in order to evaluate RNA expression in a later project.

Perspectives

Perspective 1: This study is based on the expression of selected proteins in normal pregnancies at term. A more broader gene expression profile at different times of gestational ages in relation to different pathological conditions could be interesting and done by RNAseq.

Perspective 2: We intend to conduct a large clinical trial on the use of ACM cells for identification of pregnancies at risk of adverse outcome, and investigate if the ACM cells can be used as biomarkers for early detection of threatening preterm birth.

Perspective 3: Interventions to reduce preterm labor have primarily been designed based on the signaling effects emitted by maternal compartments. By investigating the pathophysiological mechanisms of the fetal amniochorionic membrane, we will be able to tailor treatments based on signals from the fetal compartments as well. This may enable us to develop more advanced treatments in the future.

Internalization

- ARCEDI Biotech Aps: This private firm has established their primary technology for rare circulating fetal cell isolation and analysis at the laboratory at the Department of Gynecology and Obstetrics, Aarhus University Hospital, and has presently also established collaborations and laboratories in the United States.
- [name] from the Department of Gynecology and Obstetrics at University of Texas Medical Branch at Galveston is an honorary professor at Aarhus University Hospital, Department

of Gynecology and Obstetrics. Through many years of research, he has achieved profound knowledge of the fetal membranes and its pathophysiology during preterm birth.

- [name] from Medical University of Graz, Austria, has a profound knowledge of the antibody staining of placental biopsies and is internationally leading the use of this method.

Ethical aspects

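### Hypothesis 4 speaks of risk of PPROM, but PPROM and PLC women are sampled only after onset, so the group comparison can show association with established disease, not prior risk

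*Combined protocol and SAP*

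**What the plan says.** Hypothesis 4 of the project states: "The concentration of circulating ACM cells reflects the risk of certain adverse pregnancy outcomes, including Preterm Prelabor Rupture of the Fetal Membranes (PPROM". Aim 2 is softer and concerns preterm birth. It proposes "to investigate if they can function as biomarkers of amniochorionic membrane dysfunction, including risk of preterm birth".

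The groups that carry this question are in Study 3, Materials:

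- PPROM (item 4): "We will recruit 25 participants treated at the ward because of PPROM before 34 weeks gestation".
- PLC (item 3): "We will recruit 25 participants treated at the ward with tocolytics because of preterm labor contractions before 34 weeks gestation".
- Controls (item 5): "We will recruit 25 women at gestation week 25+0 to 37".
- Normal longitudinal cohort (item 1): "We will recruit 25 participants at their nuchal translucency scan at 12 weeks gestation". The schedule in pregnancy is: "Blood samples will be collected at week 12, 20, 28, 34 and 36".

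Study 2 adds 15 women with normal pregnancies, followed from week 12, and a cross-sectional cohort of 10 to 100 women in the second or third trimester.

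Three other statements bear on the point. Study 3's own hypothesis for pathological pregnancies is that the count lies above what is normal at that gestation; it says nothing of prediction. The Statistical Analysis Plan has one sentence linking the primary outcome to secondary outcomes of pregnancy and birth, which it does not define. Perspective 2 assigns to a later, large trial the task to "investigate if the ACM cells can be used as biomarkers for early detection of threatening preterm birth".

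**The concern.** A statement about risk needs a sample taken before the outcome. No sampling time is given for the PPROM and PLC groups, but study blood cannot be drawn before recruitment, and recruitment follows onset. No sample in the PPROM group precedes rupture, and none in the PLC group precedes contractions.

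The protocol itself makes the reverse direction plausible. Study 3 expects counts to rise during labor, so a high count in women with contractions may be an effect of the contractions. The Background says the route of the cells into maternal blood is unknown and names microfractures of the membranes as a possible source, so rupture could itself release cells. A difference between cases and controls cannot separate these explanations from a pre-existing risk marker.

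At stake is what a positive result may be said to show. Read against hypothesis 4, it could pass for evidence that the count signals PPROM in advance, which the comparison cannot provide.

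**Working it through.** The documents give no event rate, effect size, SD or sample-size derivation, so there is no stated figure to reproduce. All rates and splits below are assumptions.

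**1. Order of sample and outcome**

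| Group | n | Sample before PPROM or PLC? | Sample before delivery? |
|---|---|---|---|
| PPROM | 25 | No | Yes, if drawn at inclusion |
| PLC | 25 | No (not before PLC) | Yes, if drawn at inclusion |
| Study 3 controls | 25 | Not described as affected | Yes |
| Study 3 longitudinal | 25 | Yes, but labelled normal | Yes |
| Study 2 longitudinal | 15 | Yes, but labelled normal | Yes |
| Study 2 cross-sectional | 10–100 | Not described as affected | Yes |

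**2. Events expected in the women sampled serially from week 12**

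Expected events = n × p; chance of none = (1 − p)^n. Here n = 25 (Study 3) or 25 + 15 = 40 (both studies).

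| Outcome, assumed p | n = 25: expected | n = 25: none | n = 40: expected | n = 40: none |
|---|---|---|---|---|
| PPROM, 1% | 0.25 | 0.99^25 = 78% | 0.4 | 0.99^40 = 67% |
| PPROM, 3% | 0.75 | 0.97^25 = 47% | 1.2 | 0.97^40 = 30% |
| Preterm birth, 5% | 1.25 | 0.95^25 = 28% | 2.0 | 0.95^40 = 13% |
| Preterm birth, 10% | 2.5 | 0.90^25 = 7% | 4.0 | 0.90^40 = 1.5% |

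The preliminary findings in the Background are that the cells are absent in the first half of pregnancy. The week-12 sample should therefore carry little information, which leaves mainly weeks 20 and 28 in Study 3 before a PPROM under 34 weeks.

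**3. Adding the women sampled once**

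With the controls and the cross-sectional cohort, the total is 40 + 25 + 10 = 75 to 40 + 25 + 100 = 165. At 1% this gives 75 × 0.01 = 0.75 to 165 × 0.01 = 1.65 PPROM cases. These are upper limits for that rate, because a woman sampled once in mid or late pregnancy has already passed part of the period at risk. Study 2 also varies the antibodies while the method is being developed, so its counts may not be comparable with those of Study 3.

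**4. What the groups of 25 can detect**

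Normal approximation, two-sided 5%, 80% power: detectable difference in SD units = (1.960 + 0.842) × √(1/n1 + 1/n2).

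- Cases against controls, 25 v 25: 2.802 × √(0.08) = 0.79 SD. This is a difference after onset.
- Within PLC, preterm against term delivery, assumed splits: 5/20 gives 2.802 × √(0.25) = 1.40 SD; 8/17 gives 1.20 SD; 12/13 gives 1.12 SD. None of these allows for adjustment for gestational age.

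**The case against.** The strongest defence is that the operative hypothesis is the one in Study 3, which is cross-sectional, and that the design fits it. Perspective 2 defers early detection to another trial. On this reading the only fault is a loosely worded project-level hypothesis. That is largely fair, and it is why the remedy is mostly wording. It does not remove the conflict: hypothesis 4 still stands as a hypothesis of this project, and for PPROM nothing in the design can test it.

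Four stronger readings are tempting, and the documents do not support them.

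- *The design cannot address risk at all.* PLC women are recruited before delivery, and contractions need not end in preterm birth, so later preterm birth can be studied among them. The SAP sentence on birth outcomes leaves room for this.
- *Aim 2 claims that the cells reflect risk.* It proposes only to investigate, and it names preterm birth, not PPROM.
- *Only the longitudinal cohorts are sampled before onset.* The Study 3 controls and the Study 2 cross-sectional women are not described as affected when sampled. They add few expected cases, but they exist.
- *A positive comparison will be reported as confirming hypothesis 4.* No passage says so. The wording permits it, which is reason enough to settle the wording in advance.

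**Conclusion.** The point holds for hypothesis 4. The comparison of PPROM and PLC women with controls can show association with established disease, not prior risk of either condition. The women sampled before onset cannot make up for this: about 0.25 PPROM cases are expected in 25 women and 0.4 in 40 at an assumed 1%, and still only 0.75 and 1.2 at an assumed 3%.

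For Aim 2 the conclusion is weaker. Risk of preterm birth can be explored where delivery follows the sample, mainly within the PLC group, but only differences of about 1.1 to 1.4 SD would be detected with 80% power under the assumed splits.

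The conclusion about sample timing rests on the protocol text alone. The figures rest on assumed rates and splits, and the within-PLC result also on the sample being taken at inclusion. The data remain useful; the claim should be limited before results are seen.

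**What to change.** 1. **Hypothesis 4.** Align it with Study 3's own hypothesis, for example: *ACM cell concentration is higher in women with established PPROM or PLC than in controls, after adjustment for gestational age at sampling.* The adjustment is needed because controls span 25+0 to 37 weeks while cases arise before 34 weeks. Show the distribution of gestational age by group, since adjustment extrapolates where the groups do not overlap.
2. **Aim 2.** Limit the part on risk to analyses in which the outcome follows the sample, consistent with Perspective 2.
3. **SAP.** Replace the undefined sentence on birth outcomes with a named exploratory analysis within the PLC group: association of the count at inclusion with time from sample to delivery and with delivery before 37 weeks, adjusted for gestational age and reported as an estimate with a 95% CI. State that sampling is at inclusion, and list delivery date among the recorded variables; no delivery variable is named at present.

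The cost is protocol wording, one analysis and one recorded date, with no new participants or samples. The stated claim becomes less favourable, and the PLC analysis will be imprecise. A real test of PPROM risk belongs in the later trial: 25 cases sampled before onset would need about 25/0.01 = 2,500 women at an assumed 1%, or 25/0.03 ≈ 834 at 3%.

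### The labor part of Study 3 Hypothesis 1 rests on a comparison of different women, and no within-woman analysis is planned although planned longitudinal samples would allow one

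*Combined protocol and SAP*

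**What the plan says.** Study 3, Hypotheses, item 1 reads: "Normal pregnancies: The number of ACM cells depends on gestational age and increases during labor". The labor contrast is in Study 3, Materials, item 2: "We will recruit 25 women in active labor at the delivery ward and 25 women with planned cesarean sections within a few days". Item 2 does not give the number of samples per woman and lists no sample before labor for the women in labor.

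Two other planned cohorts contain repeated samples from the same women:

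- **Study 3, Materials, item 1** (25 women): "Blood samples will be collected at week 12, 20, 28, 34 and 36", then "Furthermore, we will collect blood at term, 2 days, and 4, 8 and 12 weeks after birth". The text does not say whether the term sample is taken in labor or before it.
- **Study 2, Materials, item 2** (15 women): "Blood samples will be collected in gestation weeks 12, 20, 28 and 34, as well as at labor and post partum". The Study 2 aims are antibody performance and stability of the expression pattern over gestation.

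The Statistical Analysis Plan compares the mean count between groups and gives a confidence interval for each group mean. It names no paired or repeated-measures analysis.

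**The concern.** The hypothesis concerns change within a woman; item 2 measures a difference between women. The protocol itself supplies a rival explanation. Under Background, ACM cells, aging of the membrane cells is said to end in "telomere-dependent cellular senescence, labor and human parturition". Overall Hypotheses 3 and 4 hold that the circulating count reflects membrane status and risk. If so, women who have gone into labor may have had higher counts before it began. The comparison group is also selected, since its members were scheduled for cesarean. Nor does the plan match the two groups on gestational age within term, although Hypothesis 1 itself says the count depends on gestational age.

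The explanations point in different directions for the research program. A count that is raised before labor would favor the early-detection use in Perspective 2. A count that labor itself raises is a by-product of labor. Item 2 cannot separate the two at any sample size.

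**Working it through.** **Inputs from the documents.** 25 and 25 women (Study 3, item 2); 25 women followed (Study 3, item 1); 15 women followed (Study 2, item 2); significance at p < 0.05 (SAP). The documents give no effect size, SD or power, so there is no figure to reproduce.

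**Assumptions.** Log counts approximately normal; two-sided test; log SD between women 0.6 to 1.0; within-woman correlation ρ of 0.3 to 0.7. A t-type comparison of log counts stands in for the SAP's test. Whether the SAP's named test suits mean counts is a separate matter.

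**1. Item 2 with no labor effect.** Suppose women in labor already had R times the count and labor adds nothing. The SE of the log ratio is SD × √(2/25), the expected log ratio is ln R, and the critical value is t(48) = 2.01, with a normal approximation for the probability of p < 0.05.

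| Log SD | SE | R = 1.5 (ln R = 0.405) | R = 2 (ln R = 0.693) |
|---|---|---|---|
| 0.6 | 0.170 | 65% | 98% |
| 0.8 | 0.226 | 41% | 85% |
| 1.0 | 0.283 | 28% | 67% |

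**2. Two explanations, same item 2 result.** A simulation (20,000 runs, unit SD, ρ = 0.5, t-tests) compared A, a true rise of 0.8 SD in labor, with B, a level 0.8 SD higher before labor and no rise.

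| Comparison | A: true rise | B: already higher |
|---|---|---|
| 25 versus 25 different women | 79.7% | 79.4% |
| 25 pairs, same women | 97.0% | 5.0% |
| 15 pairs, same women | 81.9% | 4.9% |

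Pairs separate A from B. The paired rows assume a pre-labor sample close to labor. The last scheduled one is week 34 in Study 2 and week 36 in Study 3 item 1 (unless its term sample is drawn before labor), so these rows show the principle and not the performance to expect.

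**3. What the planned pairs can deliver.** For the 15 Study 2 women at SD 0.8, the simple labor-to-week-34 log ratio has SE = 0.8 × √(2(1 − ρ)/15) = 0.244, 0.207 and 0.160 at ρ = 0.3, 0.5 and 0.7. That looks close to the 0.226 of item 2, but it mixes labor with later gestation.

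To allow for gestation, extrapolate each woman's slope from week 28 to week 34 up to labor, assumed at week 39. The contrast is labor − week 34 − (5/6)(week 34 − week 28), with weights 5/6, −11/6 and 1. The squared weights sum to 0.694 + 3.361 + 1 = 5.056. With equal correlations, SE = 0.8 × √(0.5 × 5.056/15) = 0.328 at ρ = 0.5.

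That is 0.328/0.226 = 1.45 times the item 2 SE. With a paired t on 14 df, power is about 21% for a true 1.5-fold rise and 50% for a 2-fold rise. The corresponding item 2 figures at SD 0.8 are 41% and 85%.

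**The case against.** Several objections carry weight.

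- **Study 3 does contain within-woman data.** A reader might infer that Study 3 only compares different women, each sampled once. The documents do not support this. Item 1 follows 25 women with a week 36 and a term sample, on the Study 3 assay. What is open is whether the term sample is drawn in labor. For item 2, a single sample per woman is itself an inference.
- **The Study 2 labor samples have a use.** A reader might infer that they go to waste. They serve the Study 2 aims, and the documents are silent on whether they also inform Study 3. What is missing is a stated use for Hypothesis 1.
- **The Study 2 pairs cannot decide the question.** It is tempting to allow a claim of an increase during labor only if those pairs show one. The figures above argue against such a gate: it would usually miss a 1.5-fold rise. The antibodies are still being varied in Study 2, and a membrane-aging process that accelerates after week 34 would pass as a labor effect even after a linear slope correction.
- **Item 2 can be read as associational.** It is headed as women with and without contractions, and the preterm question rests mainly on the groups in items 3 to 5. That the result would be reported as a rise in labor is a prediction; the plan does not say so.

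These points limit the remedy and the importance. They do not remove the gap: the hypothesis is worded as a change, its explicit labor contrast is between women, and the SAP specifies nothing else.

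**Conclusion.** The point holds in limited form. Item 2 alone cannot support the statement that the count increases during labor, because a pre-existing or selection difference gives the same result. At log SD 0.8, a 1.5-fold pre-existing difference alone would be significant in about 41% of trials, and a 2-fold difference in about 85%. These sizes rest wholly on assumed SDs and assumed prior differences. The documents do not show that any such difference exists.

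The planned longitudinal samples can add within-woman evidence, but supporting evidence only. The improvement is worthwhile because it is cheap and limits a conclusion the design cannot carry; the point does not invalidate Study 3.

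**What to change.** Make two changes to the SAP, with one data item in Study 3:

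1. State that item 2 is reported as a difference between women in labor and women not in labor, and not on its own as an increase during labor.
2. Record, for each term sample in Study 3 item 1, whether it was drawn in or before labor. Prespecify a within-woman analysis of log counts, for example a mixed model with gestational age and an in-labor indicator. Use item 1 and, where the same antibody set was used at both draws, the Study 2 labor samples. Label this analysis supportive; it is not a condition for reporting item 2.

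**Cost.** SAP wording, one recorded item and one analysis, with no new women or draws.

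**Limits.** There are few women, and the number of item 1 samples drawn in labor is unknown. Precision is low once gestational age is accounted for (SE about 0.33 on the log scale for 15 women, at assumed SD 0.8 and correlation 0.5). Study 2 antibodies may differ from the final assay. A rise in the last days before labor still cannot be separated from labor itself.

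### A PLC-control difference in ACM count cannot be told apart from a contraction effect, so it does not by itself support a marker of membrane dysfunction

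*Combined protocol and SAP*

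**What the plan says.** All places are in the combined protocol and SAP.

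- Study 3, Hypotheses, 1: "Normal pregnancies: The number of ACM cells depends on gestational age and increases during labor".
- Study 3, Hypotheses, 2: "Pathological pregnancies: The number of ACM cells is increased above the normal level for the gestational age". The reference is gestational age; contractions are not mentioned.
- Study 3, Materials, item 3 (PLC): "We will recruit 25 participants treated at the ward with tocolytics because of preterm labor contractions before 34 weeks gestation".
- Study 3, Materials, item 4 (PPROM): "We will recruit 25 participants treated at the ward because of PPROM before 34 weeks gestation". Contraction status at sampling is not stated.
- Study 3, Materials, item 5: "Control group: We will recruit 25 women at gestation week 25+0 to 37". Contraction status and matching are not stated.
- Study 3, Materials, item 2 (term women): "We will recruit 25 women in active labor at the delivery ward and 25 women with planned cesarean sections within a few days". Nothing links these two groups to the PLC result.
- Statistical Analysis Plan: group means are compared with a chi-square test at p < 0.05 and shown with 95% CIs. No contrast is named, there is no adjustment for gestational age or labor, and nothing says how a PLC excess is to be interpreted.
- Aim 2 of the project is to find out whether ACM cells can serve as a marker of membrane dysfunction, including the risk of preterm birth.

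**The concern.** PLC women differ from controls in two respects that matter here: they are contracting, and they may have a membrane disorder. The plan's own first hypothesis makes the first of these a possible cause of a raised count in healthy women. Neither the design nor the SAP holds it fixed.

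A rise caused only by contractions would still satisfy Hypothesis 2 as worded, because that hypothesis asks only whether the count exceeds normal for the week. It would not bear out Aim 2. It would also be a weak basis for the large trial of early detection foreseen under Perspective 2, since a count that rises once a woman is already contracting adds little to early detection.

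**Working it through.** **No figure to reproduce.** The documents give no mean, SD, expected difference or sample-size derivation. Everything below except the 25 per group and the 0.05 level is assumed. A two-sided test is also assumed, since sidedness is not stated. The figures describe a suitable count comparison, not the chi-square test in the SAP.

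**1. How often contractions alone would give a PLC-control difference.** Assume control mean μ = 3, negative binomial shape k = 1 or 2, n = 25 per group, no pathology, and a PLC mean of rμ.

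SE(log ratio) = √[(1/μ + 1/k)/25 + (1/(rμ) + 1/k)/25]

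Probability of significance = Φ(log r / SE − 1.96)

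For r = 2, k = 1: SE = √[(1.333 + 1.167)/25] = √0.100 = 0.316; 0.693/0.316 = 2.19; Φ(0.23) = 0.59.
For r = 2, k = 2: SE = √[(0.833 + 0.667)/25] = √0.060 = 0.245; 0.693/0.245 = 2.83; Φ(0.87) = 0.81.

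| Contraction-only ratio r | k = 1: SE, probability | k = 2: SE, probability |
|---|---|---|
| 1.5 | 0.320, 24.5% | 0.249, 37% |
| 2 | 0.316, 59% | 0.245, 81% |
| 3 | 0.313, 94% | 0.240, 99.5% |

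A simulation with a rank-sum test instead (4,000 trials per setting) gave lower figures with the same message: 18-31%, 46-73% and 83-98% for r = 1.5, 2 and 3. On a standardized scale with a two-sample comparison of means, a contraction-only rise of 0.25, 0.5, 0.8 or 1.0 SD is significant in about 14%, 42%, 81% or 94% of trials.

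**2. What the term groups can add.** The benchmark is (PLC / control) / (term active labor / term planned cesarean). With similar means in the two pairs its SE is √2 times the simple one: 0.316 × 1.414 = 0.447 (k = 1) and 0.245 × 1.414 = 0.346 (k = 2).

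- Excess detectable at 80% power: exp(2.80 × 0.447) ≈ 3.5 and exp(2.80 × 0.346) ≈ 2.6.
- Standardized scale: SE is √(4/25) = 0.40 SD against √(2/25) = 0.28 SD. The detectable difference is 1.12 SD against 0.79 SD, and power for a 0.8 SD excess is 52% against 81%. About 50 per group would be needed to bring 1.12 SD down to 0.79 SD.
- If the contraction effect is equal at term and preterm and there is no pathology, simulated rejection rates were 5.1-6.6%, close to nominal.

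**3. Where the benchmark misleads.** With four groups, SE = √[Σ(1/mean + 1/k)/25].

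- Contractions double the count in both settings and pathology doubles it again (means 12, 3, 6, 3). k = 1: √(4.917/25) = 0.443, Φ(0.693/0.443 − 1.96) = 35%. k = 2: √(2.917/25) = 0.342, giving 53%. A real doubling is missed about half the time or more.
- Preterm contractions under tocolytics add nothing, pathology doubles the count and term labor doubles it. The true benchmark is 1, so a wholly pathological rise fails to show as an excess about 97% of the time.
- No pathology, a 1.5-fold preterm effect and a 3-fold term effect (means 4.5, 3, 9, 3). The two-sided test rejects in 34% (SE 0.447) to 52% (SE 0.346), with the ratio below 1.

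**The case against.** Four stronger readings are tempting, and the documents do not support them.

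- **That the plan would read a PLC excess as pathological.** The SAP names no PLC-control contrast and states no rule of attribution. Hypothesis 2 puts the rise under pathological pregnancies but claims no cause. How the authors would report it is an inference.
- **That Hypothesis 2 follows automatically for PLC if Hypothesis 1 is true.** Hypothesis 1 concerns labor in normal pregnancies. The PLC women have preterm contractions treated with tocolytics, and nothing says these raise the count as labor does.
- **That controls are free of contractions.** This is the natural reading, but item 5 defines them by gestational week only.
- **That the term groups would separate the two causes.** They do so only if the contraction effect is similar at term and preterm, which the documents do not establish. Nor are the four groups a clean two-by-two layout: PLC women are before 34 weeks, controls run to 37, and Hypothesis 1 itself makes the count depend on gestational age.

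It can also be objected that a binding rule based on the ratio of ratios could hide the very effect sought. That stands: the calculations show low power and a bias toward concealment if term labor has the stronger effect. A partial reply is that this bias produces almost no false claims of pathology. The reverse case, a stronger preterm effect, has no such protection. PPROM women who are not contracting offer a comparison that needs no extrapolation from term, although it mixes contractions with the type of disorder.

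None of this removes the core point that contractions and pathology are not separated in the PLC comparison.

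**Conclusion.** The point holds in a limited form. On the plan's own hypotheses, a PLC-control difference has two candidate explanations that neither design nor SAP distinguishes, so it does not by itself support Aim 2. If preterm contractions alone doubled the count, such a difference would be significant in 59-81% of trials under the assumed mean of 3 and shape 1-2; a 1.5-fold effect gives about 25-37%. These figures show that the problem could be large, not that it is.

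The term groups can serve as a benchmark for the size of a labor effect. They cannot settle the cause, and their use should not become a decision rule. This is a cheap improvement to the analysis and to the wording of conclusions. It is not evidence that the study will reach a wrong answer.

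**What to change.** In the SAP:

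1. Name the PLC-control ratio with its 95% CI as the comparison for PLC, from a count model that includes gestational age.
2. Add (PLC / control) / (term active labor / term planned cesarean) with its 95% CI as a supportive benchmark. State that it assumes a similar contraction effect at term and preterm, and treat a non-significant result as inconclusive.
3. Record contraction status at sampling in the PLC, PPROM and control groups, and compare PLC women with PPROM women who are not contracting.
4. Describe a PLC excess as associated with preterm labor contractions. Claim a cause in membrane pathology only if these comparisons support it.

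Cost: analysis work, SAP wording and one more recorded item. All the groups are already planned, and no added recruitment is proposed. The price is precision: the benchmark's SE is about 1.4 times that of the simple ratio (0.35-0.45 on the log scale under the stated assumptions), and it can hide a true excess if term labor has the stronger effect. The number of non-contracting PPROM women is unknown and at most 25.
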